If medications are dispensed in a blister package, if possible, study participants will be asked to place blister packages into medication bottles and take as above. Because most AYAs can take tablets, use of liquid formulations will be rare. However, when indicated or requested by patients, pharmacists will dispense oral, crushable tablets for compounding. Those study participants will, however, be asked to open their MEMS bottle at the same time as taking their GVHD medication. Patients will be instructed not to open the container unless taking a dose of the medication and to remove only the prescribed dose. After the final 6 months of study participation, study participants will be asked to return their MEMS track cap to their study coordinator.

9.6 Data collection schedule for study staff.

Caregiver reported costs of care and medical record data will be collected monthly (Figure 3). Details about staff-data collection are as follows:

Figure 3. Schedule of Study Activities by Month Post-Enrollment

Month	0	1	2	3	4	5	6
	P	P	P	P	B	B	B
	S				S		S
PRISM	PS	PS-a	PS-a	PS	PS-a	PS-a	PS
	M	M	M	M	M	M	M
	HR	HR	HR		HR		HR
	BS	BS			BS		
-Digital MEMS cap monitoring -							
Enrollment and Randomization	S			S			S
	PS	PS-a	PS-a	PS	PS-a	PS-a	PS
Usual Care	M	M	M	M	M	M	M
	HR	HR	HR		HR		HR
	BS	BS			BS		
-Digital MEMS cap monitoring -							

LEGEND: P=PRISM Session, B=PRISM Booster, S=Survey, PS = Parent Survey, PS-a = Parent Survey, abbreviated, M=Medical Record Abstraction, HR=Heart Rate Variability, BS = Blood Sample

9.6.1 Digital pharmaco-adherence. Medical record abstraction will include prescription details including medication-name, frequency, and dosing.

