11.5 Exploratory Analyses

11.5.1 **Digitally (MEMS-cap) assessed medication adherence rates** will be defined as [(# events of MEMS cap opening/# events prescribed)] x 100. Days when oral GVHD medications were held by the prescriber (captured via medical record abstraction) will be removed from the denominator, whereas “missed doses” will be defined as those where no cap was opened on a day medication was prescribed. Adherence will be calculated on a monthly basis and summarized both monthly, and as a 3-month average.

11.5.2 We will calculate **incremental cost consequence ratios** (e.g., the cost for each unit of improvement in average HADS scores or adherence) using the same costing numerators as above with the HADS and adherence change as the denominator. These will be included not as a threshold for cost-effectiveness, but as part of a comprehensive evaluation of both costs and consequences of the intervention.

11.5.3 **To explore the contribution of different cost parameters to total healthcare costs**, we will analyze disaggregated costs (e.g., formal-, informal-, and non-healthcare sector costs) from a payer and societal perspective.^{78,139} A similar analysis will be completed from the societal perspective. An incremental analysis will estimate the arithmetic mean difference in costs between intervention and control patients using multivariable generalized linear analytic techniques to adjust for variability in outcomes based on baseline characteristics. Sensitivity analyses will model the potential range of cost impact based on variable fee-for-service and out-of-pocket expenses

To explore family experience scores, we will conduct descriptive analyses of categorical data. Comparisons will include standard hypothesis testing including chi-square tests for frequency data and Kruskal Wallis for non-parametric differences in distribution of responses.

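### The MEMS adherence rate in section 11.5.1 puts no ceiling on counted openings, and its missed-dose definition works by day while the rate works by dose

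*Combined protocol and SAP*

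**What the plan says.** Section 11.5.1 defines the adherence rate as "events of MEMS cap opening/# events prescribed)] x 100". It makes one adjustment: days on which the prescriber held the oral GVHD drug "will be removed from the denominator". It does not say what happens to any opening recorded on such a day. The same sentence then defines missed doses as those where "no cap was opened on a day medication was prescribed". On reporting it says: "Adherence will be calculated on a monthly basis and summarized both monthly, and as a 3-month average".

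Two other sections bear on the point. Section 9.5 states that the device logs the date and time of each opening. It tells patients to open the bottle only to take a dose and to refill it only when a dose is due. Section 9.6.1 states that chart abstraction covers "prescription details including medication-name, frequency, and dosing". The number of doses per day is not given anywhere.

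Adherence is the outcome of exploratory aim 1.5.1. It also enters the cost-consequence ratio in section 11.5.2 and the effect-modification analyses in section 11.6.

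**The concern.** The numerator is a raw count of openings. Nothing ties an opening to a particular dose or day, so an extra opening on one day carries the same weight as a dose taken on another. This has two consequences: a rate above 100% is possible, and a rate of 100% does not mean that every dose had an opening.

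The second difficulty is the unit. The rate counts prescribed events, so it is sensitive to one of two daily doses being left out. The missed-dose definition asks only whether the day had any opening at all, so it cannot see that omission.

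What is at stake is the meaning of an exploratory outcome and of the analyses that use it. With no rule written down, an analyst who meets rates above 100% would have to choose a truncation after seeing the data.

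**Working it through.** The plan gives no expected adherence rate or worked example, so there is no figure of its own to reproduce. The check applies the two definitions literally to simple patterns of opening.

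**Inputs.** Rate, held-day rule and missed-dose definition: section 11.5.1. Month length: 30 days, assumed. Doses per day, k: not stated, so k = 1, 2 and 3 are assumed to show the range. Section 11.5.1 counts prescribed events and section 9.6.1 abstracts frequency, so the plan allows for more than one dose a day.

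**Formulas.** Let o be the openings on a given day.
- Rate as written = 100 × sum(o) / (30k)
- Missed by the day rule = number of days with o = 0
- Capped rate = 100 × sum(min(o, k)) / (30k)
- Missed by dose = sum(max(k − o, 0))

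**Results.**

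| Pattern over 30 days | k | Rate as written | Days missed | Capped rate | Doses missed |
|---|---|---|---|---|---|
| All doses plus 3 extra openings | 1 | 33/30 = 110.0% | 0 | 100.0% | 0 of 30 |
| | 2 | 63/60 = 105.0% | 0 | 100.0% | 0 of 60 |
| | 3 | 93/90 = 103.3% | 0 | 100.0% | 0 of 90 |
| 5 days none, 5 days doubled, 20 exact | 1 | (0+10+20)/30 = 100.0% | 5 | 25/30 = 83.3% | 5 of 30 |
| | 2 | (0+20+40)/60 = 100.0% | 5 | 50/60 = 83.3% | 10 of 60 |
| | 3 | (0+30+60)/90 = 100.0% | 5 | 75/90 = 83.3% | 15 of 90 |
| 15 days with one opening, 15 with three | 2 | (15+45)/60 = 100.0% | 0 | (15+30)/60 = 75.0% | 15 of 60 |
| One opening every day | 1 | 30/30 = 100.0% | 0 | 100.0% | 0 of 30 |
| | 2 | 30/60 = 50.0% | 0 | 50.0% | 30 of 60 |
| | 3 | 30/90 = 33.3% | 0 | 33.3% | 60 of 90 |
| 10 days none, 20 exact | 2 | 40/60 = 66.7% | 10 | 66.7% | 20 of 60 |

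**Reading the table.**
1. Rates above 100% and the cancelling of omissions by surplus openings do not need a multi-dose regimen; both appear at k = 1. In the second pattern 5k of 30k doses (16.7%) had no opening on their day, whatever k is.
2. The mismatch between day and dose does need k of 2 or more. It arises without any stray opening: at k = 2, one opening a day gives 50% and zero missed.
3. When only whole days are omitted and there are no extra openings, the definitions agree: 10 of 30 days missed is 33.3%, the complement of 66.7%.
4. After capping, the rate always equals 100 × (1 − doses missed / doses prescribed), so the two measures cannot disagree.

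**Held days.** An opening on a held day adds to the numerator with nothing to match it below. At k = 1, with one held day, one opening on it and all else exact, the literal rate is 30/(30 − 1) = 103.4%.

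**The case against.** The strongest reply is that section 9.5 controls the problem at source. Patients are told to open only at dose time. A refill done as instructed happens during a dose opening and so adds none. Coordinators make monthly contact, and section 13.7.2 adds calls after discharge and after later admissions. This stands as a reason to expect fewer surplus openings. It does not say how to count those that occur, and it does nothing about the day-versus-dose mismatch.

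A second reply is that the missed-dose clause may not be a separate measure. It is set against the held-day rule, and can be read as saying only that held days come out of the denominator while unopened prescribed days stay in. That reading is fair, and section 11.5.1 announces no summary of missed doses. The definition is nevertheless worded by day, and it conflicts with the rate if anyone uses it.

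A third reply is that the patterns above are constructed. That is so. They show what the definitions permit, not what will be seen, and an opening counted as surplus might be a late or make-up dose.

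Finally, a daily cap is itself a proxy, with errors of its own. This also stands; the errors are listed with the fix.

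**Conclusion.** The definitional gap is real and small. Followed literally, section 11.5.1 allows rates above 100%, lets surplus openings offset omitted doses, and leaves a missed-dose definition that disagrees with the rate when part of a day's doses is omitted. The sizes rest on a 30-day month and assumed dosing frequencies. The frequency of surplus openings is unknown.

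Three stronger readings are tempting, and the documents do not support them.
- **Bias between arms.** A reader might infer that booster contacts lead PRISM patients to handle the bottle more. Section 9.4 describes boosters as practice of resilience skills and does not link them to the bottle; Figure 3 shows MEMS monitoring in both arms.
- **Opposite rankings of patients in the reported results.** This would need a second reported summary, of missed doses, and none is planned.
- **A general upward bias.** Surplus openings raise the rate, but taking out several doses at one opening lowers it. The net direction cannot be stated.

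Adherence is an exploratory aim and an optional component, open only to allogeneic recipients. Section 11.5.2 says that its cost-consequence ratios are not a threshold for cost-effectiveness. The primary HADS analysis is untouched. Settling this would be a useful clarification; nothing in the trial's main conclusion depends on it.

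**What to change.** In section 11.5.1:
- Count openings by day, up to the number of doses prescribed that day, and count none on prescriber-held days.
- Define adherence as the sum of these capped openings over prescribed doses, times 100.
- Define missed doses as prescribed doses minus capped openings.
- Report surplus openings separately, so that the cap hides nothing.

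The cost is a short change of text and a few lines of code. Time-stamped openings and prescribed frequency are already collected, and no dosing or clinical rule changes.

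There are three drawbacks to accept. A calendar-day cap can discard a late dose taken after midnight. It does not correct for several doses taken out at one opening. It still credits a stray opening on a partly dosed day.

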
1.2 Purpose of the Study Protocol

The protocol is intended to be used by all study staff as the approved procedures for conduct of the study.

1.3 Primary Aim: Evaluate the effect of PRISM compared to usual care on symptoms of anxiety and depression.

Primary Outcome Measure: AYA-reported mixed affective (anxiety and depression) symptoms 6-months post enrollment (measured with the Hospital Anxiety and Depression Scale).¹

Primary Hypothesis: PRISM will be associated with lower anxiety and depression compared to usual care.

1.4 Secondary Aims:

1.4.1 Evaluate PRISM's impact on other key patient-reported outcomes 6-months following enrollment.

Outcome Measures: (a) Symptom Burden (measured by the Memorial Symptom Assessment Score)²; (b) Health-Related Quality of Life (measured with the Pediatric Quality of Life [PedsQL] 4.0 Generic and 3.0 Cancer Modules)^{3,4}; (c) Hopeful patterns of thought (Hope Scale)⁵; and, (d) resilience (Connor Davidson Resilience Scale, CDRISC-10).^{6,7}

Hypothesis: PRISM will be associated with (a) lower total symptom burden; (b) *higher* quality of life; (c) higher hope; and (d) higher resilience, compared to usual care.

1.4.2 Evaluate the cost-effectiveness of the PRISM intervention.

Outcome Measure: Cost per Quality Adjusted Life Years (QALY)

Expected findings: PRISM will be cost-effective compared to usual care, considering a standard willingness to pay threshold of \$150,000 per QALY gained

Exploratory Outcomes: (i) PRISM's cost utility as a function of treatments related to patient-reported anxiety and depression; and, (ii) PRISM's cost per clinically relevant consequence such as change in mental health score or adherence.

1.4.3 Evaluate the impact of PRISM on parent outcomes 6-months following enrollment.

Outcome Measures: Health-Related Quality of Life (SF-36)⁸; anxiety (Generalized Anxiety Disorder Screener, GAD-7),⁹ and depression (PHQ-8),^{10,11}

Hypothesis: Parents of AYAs who receive PRISM will report higher quality of life and lower psychological distress compared to parents of AYAs in usual care.

Exploratory Outcome: Family Experience (selected items from Hospital Consumer Assessment of Healthcare Providers and Systems [HCAHPS] survey).¹²

1.4.4 Describe individual and group 6-month trajectories for patient reported outcomes of usual care and PRISM participants.

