9.0 Procedures Involved

9.1 Enrollment. Once consent documents are signed and all questions addressed, the consenting RA or study staff will register the patient in the RedCap System. Randomization will not occur until after the baseline Resilience in Pediatric Cancer Assessment (RPCA) surveys are collected (see below). Site RAs will maintain original copies of all consent forms and fax/email copies to the coordinating center for secure storage and tracking purposes.

9.2 Randomization.
 As a quality control measure, a randomization log will be maintained at SCH to track the participant ID, stratum, randomized assignment, and date of randomization. Patients will be randomized only after completion of the baseline surveys and in a 1:1 ratio to receive usual, non-directive, supportive care without PRISM (“control” arm) or with PRISM (“experimental” arm). Randomization will be stratified by age (patients ages 12-17 versus ages 18-24 and site). Biostatisticians who will conduct data analysis will be blinded from the treatment group allocations. Throughout the screening period until allocation of the control or PRISM, participants will be assigned a screening number, according to the chronological order of screening. Once enrolled, the participant will be assigned a study ID.

9.3 Scheduling of study procedures with participants.

9.3.1 Baseline Survey Completion Upon enrollment, study staff will deliver the baseline survey in participant's preferred language (English or Spanish). For both English and Spanish, the study will first be offered by email via REDCap or via

REDCap on a study team iPad. Upon request, staff will offer paper-pencil versions and/or interview-based versions (interviews only available in English).

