9.8.3.3 Medical Outcomes Study 36-item Health Survey (SF-36). The SF-36 is the most widely used generic measure of HRQOL among U.S. Adults.⁸⁰ It incorporates 8 concepts: physical functioning, body pain, limitations due to physical health problems, role limitations due to personal or emotional problems as well as emotional well-being and social functioning, energy, fatigue and general health perceptions. It includes a single item regarding perceived change in health.⁸ Internal reliability ranges from $\alpha=0.78-0.93$. This instrument will only be included only full (non-abbreviated) RPCA surveys.

9.8.3.4 Hospital Consumer Assessment of Healthcare Providers and Systems (HCAHPS). This survey is a widely used and standardized tool to measure patient and family perspectives on hospital care.¹² It has been endorsed by the National Quality Forum (NQF) in order to allow for cross-hospital

comparisons. The survey includes a core set of questions that can also be combined with customized project- or site-specific items. For this study, we have included a small subset of questions from domains regarding care for teenaged patients, communication and child-centered care, and overall hospital ratings. All items are scored on a Likert Scale (for example, to the question "During this hospital stay, how often did providers involve your child in discussions about his or her health care?" response options include "Never," "Sometimes," "Usually," and "Always." This instrument will only be included only full (non-abbreviated) RPCA surveys.

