11.0 Data Analysis/Management

11.1 Overview

The primary statistical analyses will be intention-to-treat to avoid confounding by non-random participant attrition or crossover. Demographics, clinical characteristics, items within the RPCA, adherence data, and costing data will all be summarized at each time-point using descriptive statistics: frequencies and proportions for categorical variables, means and standard deviations for continuous variables, or median and interquartile range if distribution is skewed. All analyses will be adjusted for patient age and site, as randomization is stratified by age and site, as well as baseline characteristics clearly imbalanced between groups. Additional baseline characteristics we consider as potential confounders include sex, race, and primary language spoken at home.

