11.3 Randomization

The randomization algorithm will be constructed by the study statistician using a permuted blocks scheme with randomly varying block sizes, within strata defined by age group and sites. Randomized assignments will be administered by a research associate using REDCap. Randomization will be stratified by age (patients ages 12-17 versus ages 18-24) and site.

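### The family-experience (HCAHPS) tests in 11.5.3 ignore age group and site although 11.1 promises adjustment for both; if responses differ by hospital they are conservative and lose power

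*Combined protocol and SAP*

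**What the plan says.** Section 11.1 sets a general rule and gives its reason: "All analyses will be adjusted for patient age and site, as randomization is stratified by age and site". It makes no exception for exploratory outcomes. Section 11.3 confirms the design, a "permuted blocks scheme with randomly varying block sizes, within strata defined by age group and sites", and Section 9.2 gives the allocation as 1:1. Two age groups and four sites make eight strata.

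Family experience is listed under the parent-outcome aim in Section 1.4.3, but only as exploratory: "Exploratory Outcome: Family Experience (selected items from Hospital Consumer Assessment of Healthcare Providers and Systems [HCAHPS] survey". Section 9.8.3.4 describes the source survey as "endorsed by the National Quality Forum (NQF) in order to allow for cross-hospital" comparisons, says a small subset of its questions is used, including overall hospital ratings, and states "All items are scored on a Likert Scale", with a four-level ordered example.

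The analysis is in the closing paragraph of Section 11.5.3. It opens "To explore family experience scores, we will conduct descriptive analyses of categorical data" and adds hypothesis tests: "chi-square tests for frequency data and Kruskal Wallis for non-parametric differences in distribution of responses". No stratified version and no covariate is mentioned. Section 11.4.3 applies the covariate-adjusted regression to the parent outcomes without saying whether the exploratory family-experience items are included.

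**The concern.** Two things are at stake.

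The first is pre-specification. An analyst following 11.1 would adjust; one following 11.5.3 would not. Either result could be reported as the planned one.

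The second is efficiency. Blocking within site makes the arms similar in site mix, so differences between hospitals contribute little to the chance difference between arms. An unstratified test still counts those differences as noise. Its reference variance is then too large, its true type I error falls below the nominal level, and it misses real differences more often than a stratified test. HCAHPS items ask about the hospital, so site is a natural source of variation for this outcome.

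**Working it through.** **The plan's own figure.** The documents give no power or sample size for the HCAHPS items. The nearest figure is for HADS in Section 11.2: 35 per arm, SD 6.2, 80% power, 5% type I error, detectable difference 4.2. By the normal formula, 6.2 × (1.960 + 0.842) × √(2/35) = 4.15; by the t-test it is 4.21. The figure reproduces. It is used here only to supply an effect scale: 4.2/6.2 = 0.68 SD.

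**Expected direction.** Let ρ be the share of response variance due to site. With perfect balance by site, the true variance of the arm difference is about (1 − ρ) times the variance an unstratified test assumes. Two-sided type I error is then about 2 × [1 − Φ(1.96/√(1 − ρ))]:

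- ρ = 10%: 1.96/0.949 = 2.07, giving 3.9%
- ρ = 20%: 1.96/0.894 = 2.19, giving 2.8%
- ρ = 30%: 1.96/0.837 = 2.34, giving 1.9%

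Incomplete blocks, dropout and grouping into categories weaken this, so simulated values should lie between these figures and 5%.

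**Simulation inputs.**

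- From the documents: 90 randomised and 70 analysed (Section 11.2); site shares 11:7:6:6 (enrolled per year, Table 3); permuted blocks in eight strata (Section 11.3); 1:1 allocation (Section 9.2); one four-category item (Section 9.8.3.4).
- Assumed: blocks of 2 and 4, equal age groups, no age effect, a normal latent response, dropout at random, and ρ from 0 to 30%.
- There were 9,000 trials per setting. Monte Carlo standard error is about 0.002 for type I error and 0.005 for power.

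Kruskal-Wallis (KW) against a van Elteren (VE) test stratified by site, with an arm difference of 0.68 SD for power:

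| Site share ρ | Type I, KW | Type I, VE | Power, KW | Power, VE | Power lost by KW |
|---|---|---|---|---|---|
| 0% | 0.049 | 0.051 | 0.694 | 0.685 | none (0.009 gained) |
| 5% | 0.049 | 0.053 | 0.699 | 0.705 | about 0.01 |
| 10% | 0.047 | 0.051 | 0.697 | 0.719 | 0.022 |
| 20% | 0.032 | 0.045 | 0.694 | 0.765 | 0.07 |
| 30% | 0.025 | 0.046 | 0.685 | 0.799 | 0.114 |

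Chi-square (top category against the rest) and Cochran-Mantel-Haenszel by site show the same pattern in power: 0.601 against 0.605 at 0%, 0.598 against 0.628 at 10%, 0.590 against 0.651 at 20%, and 0.580 against 0.675 at 30%. Chi-square type I error falls to about 0.035 at 20–30%.

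**Cost of stratifying by both factors.** The table stratifies by site only. Repeating the simulation with van Elteren over all eight age-by-site cells (6,000 trials, ρ = 0, no age effect) gave power 0.670, against 0.693 for Kruskal-Wallis and 0.683 for site-only stratification. When nothing is gained, the cost is therefore about 1 point for site alone and about 2 points for the full cross-classification. At ρ = 20% the eight-cell test still gained about 5 points (0.743 against 0.695).

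**The case against.** The strongest reply is that little depends on this. Family experience is exploratory, is introduced as descriptive, has no stated hypothesis and does not appear in Table 7. Parent participation is optional (note after Section 3.2.1), so even 70 parents may be optimistic. Simple unadjusted tests are common for such items. All of this stands and limits the weight of the point.

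A second reply is that the named tests are given as inclusions rather than a closed list, and that 11.1 and 11.4.3 might already cover an adjusted analysis. This stands in part: the wording leaves room, but no adjusted version is named, so the ambiguity remains.

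A reader might also infer more than the documents support:

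- **That the tests are conservative as a matter of fact.** They are only if responses differ by site or age group. Section 9.8.3.4 makes a hospital effect plausible but gives no size, and at or below about 10% of variance the loss is at most 2 to 3 points.
- **That the loss is very large.** It can be made so. With sites spread over ±2 logits and an arm log-odds of 1.2, one simulation gave 50% power unstratified against 74% stratified. Nothing in the documents supports so wide a spread.
- **That the plan throws away the ordering of the responses.** Chi-square does, but Kruskal-Wallis is named in the same sentence and uses it.
- **That false positives would rise.** The error runs the other way.

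**Conclusion.** The inconsistency between 11.1 and 11.5.3 is in the text and does not depend on any assumption. Its statistical consequence is conditional. It ranges from no loss when site is unrelated to the answers, through about 2 points of power at a 10% site share, to about 7 points at 20% and 11 points at 30%, with type I error falling to about 3% and 2.5% in the last two cases. These figures rest on assumed site effects, a 0.68 SD arm difference borrowed from the HADS calculation, and 70 responding parents. The point is minor: it concerns one exploratory outcome and leaves the primary and secondary conclusions untouched. It is still worth correcting, because analysing by the randomisation strata needs no new data and costs little when it does not help.

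**What to change.** In 11.5.3, replace the unadjusted between-arm tests with one of the following:

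- proportional-odds regression of each HCAHPS item on arm, age group and site; or
- tests stratified by both age group and site: van Elteren for ordered items and Cochran-Mantel-Haenszel for unordered ones.

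Stratifying by site alone would not meet 11.1, which also promises adjustment for age. The regression enters age group and site as separate terms and so avoids splitting about 70 parents into eight cells. The descriptive summaries can stay as they are.

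If unadjusted tests are intended, 11.1 should instead exempt these items explicitly. That removes the contradiction but not the possible loss of power.

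The cost is one sentence and no new data. If site and age are unrelated to the responses, the stratified rank test gives up about 1 point of power (site only) to 2 points (all eight cells). If fewer than 70 parents take part, sparse strata or rarely used response categories may need collapsing, and the collapsing rule should be written down before arm-level data are seen.
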